#### 8.1.1. Liver Chemistry Stopping Criteria

[figure not shown]
**Liver chemistry stopping and increased monitoring criteria** have been designed to assure participant safety and evaluate liver event aetiology (in alignment with the Food and Drug Administration [FDA] premarketing clinical liver safety guidance). These protocol guidelines are in alignment with FDA premarketing clinical liver safety guidance:

<http://www.fda.gov/downloads/Drugs/GuidanceComplianceRegulatoryInformation/Guidances/UCM174090.pdf>.

Discontinuation of study treatment for abnormal liver tests should be considered by the investigator when a participant meets one of the conditions outlined in the algorithm in [Figure 2](#), or if the investigator believes that it is in the best interest of the participant.

Study treatment will be discontinued **for a participant** if liver chemistry stopping criteria are met:

**Figure 2      Phase I Liver Chemistry Stopping Criteria – Liver Stopping Event Algorithm**

Liver Safety Required Actions and Follow up Assessments Section can be found in [Appendix 3](#).

### 8.1.2. QTc Stopping Criteria

The *same* QT correction formula must be used for each individual participant to determine eligibility for and discontinuation from the study. This formula may not be changed or substituted once the participant has been enrolled.

- For example, if a participant is eligible for the protocol based on QTcB, then QTcB must be used for discontinuation of this individual participant as well.
- Once the QT correction formula has been chosen for a participant's eligibility, the *same formula* must continue to be used for that participant *for all QT corrected (QTc) data being collected for data analysis*. Safety ECGs and other non-protocol specified ECGs are an exception.

The QTcB should be based on single QTcB values of ECGs obtained over a brief recording period.

See the SoA for data to be collected at the time of treatment discontinuation and follow-up and for any further evaluations that need to be completed.

A participant that meets either of the bulleted criteria below will be withdrawn from study treatment.

- QTc, QTcB, >500 msec,

- Change from baseline: QTc >60 msec

See the SoA for data to be collected at the time of treatment discontinuation and follow-up and for any further evaluations that need to be completed.

### **8.1.3. Temporary Discontinuation**

Participants withdrawn from study treatment, will continue in the study until completion of the follow up visit for the study period.

## **8.2. Withdrawal from the Study**

- A participant may withdraw from the study at any time at his/her own request, or may be withdrawn at any time at the discretion of the investigator for safety, behavioural, compliance or administrative reasons.
- If the participant withdraws consent for disclosure of future information, the sponsor may retain and continue to use any data collected before such a withdrawal of consent.
- If a participant withdraws from the study, he/she may request destruction of any samples taken and not tested, and the investigator must document this in the site study records.
- Refer to the SoA for data to be collected at the time of study discontinuation and follow-up. Additional assessments may be performed at the discretion of the investigator.

## **8.3. Lost to Follow Up**

A participant will be considered lost to follow-up if he or she repeatedly fails to return for scheduled visits and is unable to be contacted by the study site.

The following actions must be taken if a participant fails to return to the clinic for a required study visit:

- The site must attempt to contact the participant and reschedule the missed visit as soon as possible and counsel the participant on the importance of maintaining the assigned visit schedule and ascertain whether or not the participant wishes to and/or should continue in the study.
- Before a participant is deemed lost to follow up, the investigator or designee must make every effort to regain contact with the participant (where possible, 3 telephone calls and, if necessary, a certified letter to the participant's last known mailing address or local equivalent methods). These contact attempts should be documented in the participant's medical record.
- Should the participant continue to be unreachable, he/she will be considered to have withdrawn from the study with a primary reason of lost to follow-up.

## 9. STUDY ASSESSMENTS AND PROCEDURES

Study procedures and their timing are summarized in the SoA.

- Protocol waivers or exemptions are not allowed
- Immediate safety concerns should be discussed with the sponsor immediately upon occurrence or awareness to determine if the participant should continue or discontinue study treatment.
- Adherence to the study design requirements, including those specified in the SoA, is essential and required for study conduct.
- All screening evaluations must be completed and reviewed to confirm that potential participants meet all eligibility criteria. The investigator will maintain a screening log to record details of all participants screened and to confirm eligibility or record reasons for screening failure, as applicable. During screening the following will be completed:
  - Demographic parameters will be captured: Year of birth, sex, race and ethnicity.
  - Medical /Medication /family history will be assessed as related to the inclusion/exclusion criteria in Section 6.
- Procedures conducted as part of the participant's routine clinical management (e.g., blood count) and obtained before signing of ICF may be utilized for screening or baseline purposes provided the procedure met the protocol-specified criteria and was performed within the time frame defined in the SoA.
- Blood samples will be collected as per SoA.
  - The maximum amount of blood collected from each participant over the duration of the study, including any extra assessments that may be required, will not exceed 500 mL.
  - Repeat or unscheduled samples may be taken for safety reasons or for technical issues with the samples.
  - Samples will be destroyed within 6 months after the clinical execution of the study has been completed.

### 9.1. Efficacy Assessments

Not applicable.

### 9.2. Adverse Events

The definitions of an AE or SAE can be found in [Appendix 4](#).

The investigator and any designees are responsible for detecting, documenting, and reporting events that meet the definition of an AE or SAE and remain responsible for following up AEs that are serious, considered related to the study treatment or the study, or that caused the participant to discontinue the study treatment /study (see Section 8).

### **9.2.1. Time Period and Frequency for Collecting AE and SAE Information**

- All SAEs will be collected from the time a participant consents to participate in the study until the follow-up visit at the time points specified in the SoA (Section 2).
- AEs will be collected from the start of IP administration and until the follow-up contact at the time points specified in the SoA (Section 2).
- Medical occurrences that begin before the start of study treatment but after obtaining informed consent will be recorded on the Medical History/Current Medical Conditions section of the case report form (CRF) not the AE section.
- All SAEs will be recorded and reported to the sponsor or designee within 24 hrs, as indicated in [Appendix 4](#). The investigator will submit any updated SAE data to the sponsor within 24 hrs of it being available.
- Investigators are not obligated to actively seek AEs or SAEs in former study participants. However, if the investigator learns of any SAE, including a death, at any time after a participant has been discharged from the study, and he/she considers the event to be reasonably related to the study treatment or study participation, the investigator must promptly notify the sponsor.

The method of recording, evaluating, and assessing causality of AEs and SAEs and the procedures for completing and transmitting SAE reports are provided in [Appendix 4](#).

### **9.2.2. Method of Detecting AEs and SAEs**

Care will be taken not to introduce bias when detecting AE and/or SAE. Open-ended and non-leading verbal questioning of the participant is the preferred method to inquire about AE occurrence.

### **9.2.3. Follow-up of AEs and SAEs**

After the initial AE/SAE report, the investigator is required to proactively follow each participant at subsequent visits/contacts. All SAEs, and non serious AEs of special interest (as defined in Section 3.3.1), will be followed until the event is resolved, stabilized, otherwise explained, or the participant is lost to follow-up (as defined in Section 8.3). Further information on follow-up procedures is given in [Appendix 4](#).

### **9.2.4. Regulatory Reporting Requirements for SAEs**

- Prompt notification by the investigator to the sponsor of a SAE is essential so that legal obligations and ethical responsibilities towards the safety of participants and the safety of a study treatment under clinical investigation are met.
- The sponsor has a legal responsibility to notify both the local regulatory authority and other regulatory agencies about the safety of a study treatment under clinical investigation. The sponsor will comply with country-specific

regulatory requirements relating to safety reporting to the regulatory authority, IRB/ IEC, and investigators.

- Investigator safety reports must be prepared for suspected unexpected serious adverse reactions (SUSAR) according to local regulatory requirements and sponsor policy and forwarded to investigators as necessary.
- An investigator who receives an investigator safety report describing a SAE or other specific safety information e.g., summary or listing of SAE) from the sponsor will review and then file it along with the Investigator's Brochure and will notify the IRB/IEC, if appropriate according to local requirements.

#### **9.2.5. Pregnancy**

- Details of all pregnancies in female participants and, if indicated, female partners of male participants will be collected from the start of study treatment until 5 days after the last dose or until the follow up visit where indicated.
- If a pregnancy is reported, the investigator should inform GSK within 24 hrs of learning of the pregnancy and should follow the procedures outlined in [Appendix 1](#).
- Abnormal pregnancy outcomes (e.g., spontaneous abortion, fetal death, stillbirth, congenital anomalies, ectopic pregnancy) are considered to be a SAE.

#### **9.3. Treatment of Overdose**

For this study, any dose of study treatment GR37547 or comparator greater than 500 mg ciprofloxacin within a 24-hr time period will be considered an overdose. Symptomatic and supportive treatment is recommended.

In the event of acute excessive oral over dosage, routine emergency measures must be followed. In addition, ECG, renal function and urine pH should be monitored.

Administer magnesium or calcium containing antacids which reduce the absorption of ciprofloxacin. Adequate hydration must be maintained. The administration of activated charcoal as soon as possible after oral overdose may prevent excessive increase of systemic ciprofloxacin exposure. The principal investigator will be responsible for the appropriate medical management of any participant who has an overdose.

In the event of an overdose, the investigator/treating physician should:

1. Contact the Medical Monitor immediately.
2. Closely monitor the participant for AE/SAE and laboratory abnormalities until ciprofloxacin can no longer be detected systemically (at least 3 days).
3. Obtain a plasma sample for PK analysis within 3 days from the date of the last dose of study treatment if requested by the Medical Monitor (determined on a case-by-case basis).
4. Document the quantity of the excess dose as well as the duration of the overdosing in the CRF.

Decisions regarding dose interruptions or modifications will be made by the investigator in consultation with the Medical Monitor based on the clinical evaluation of the participant.

## **9.4. Safety Assessments**

Planned time points for all safety assessments are provided in the SoA (Section 2). Additional time points for safety tests (such as vital signs, physical exams and laboratory safety tests) may be added during the course of the study based on newly available data to ensure appropriate safety monitoring.

### **9.4.1. Physical Examinations**

- A complete physical examination will include, at a minimum, assessments of the Skin, Cardiovascular, Respiratory, Gastrointestinal and Neurological systems. Height and weight will also be measured and recorded.
- A brief physical examination will include, at a minimum, assessments of the skin, lungs, cardiovascular system, and abdomen (liver and spleen).
- Investigators should pay special attention to clinical signs related to previous serious illnesses.

### **9.4.2. Vital Signs**

- Temperature, pulse rate, respiratory rate, and BP will be assessed.
- Blood pressure and pulse measurements will be assessed in a supine position with a completely automated device. Manual techniques will be used only if an automated device is not available.
- Vital signs will be measured in a supine position after 5 minutes rest and will include temperature, systolic and diastolic BP, respiratory rate and pulse. Three readings of BP and pulse will be taken. The first reading should be rejected. The second and third readings should be averaged to give the measurement to be recorded in the CRF.
- Participants will not be dosed if their average pre-dose SBP on Day 1 is <95 mm Hg or their average resting ventricular rate is  $\leq 45$  beats per minute.
- Pre-dose vital signs will be collected at -2.00 to 0.00 hrs. Following completion of the pre-dose procedures the appropriate dose of study medication will be administered.

Vital signs post dose will be obtained within  $\pm 30$  min.

### **9.4.3. Electrocardiograms**

Single 12-lead ECGs will be obtained at the Screening visit, Day 1 (to co-incide with  $t_{max}$ ), and on Day 2 at the time of discharge, as outlined in the SoA (see Section 2) using an ECG machine that automatically calculates the heart rate and measures PR, QRS, QT,

and QTc intervals. Refer to Section 8.1.2 for QTc withdrawal criteria and additional QTc readings that may be necessary.

#### **9.4.4. Clinical Safety Laboratory Assessments**

- All clinical laboratory assessments will be performed by the local laboratory.
- Refer to [Appendix 5](#) for the list of clinical laboratory tests to be performed and to the SoA for the timing and frequency.
- The investigator must review the laboratory results, document this review, and record any clinically relevant changes occurring during the study in the AE section of the CRF or equivalent. Clinically significant abnormal laboratory findings are those which are not usually expected in a healthy volunteer.
- All laboratory tests with values considered clinically significantly abnormal during participation in the study or within 7 days after the last dose of study treatment should be repeated until the values return to normal or baseline or are no longer considered significantly abnormal by the investigator or medical monitor.
- If such values do not return to normal/baseline within a period of time judged reasonable by the investigator, the aetiology should be identified and the sponsor notified.
- All protocol-required laboratory assessments, as defined in [Appendix 5](#), must be conducted in accordance with the PAREXEL laboratory manual, PAREXEL standard operating procedures (SOPs) and the SoA.
- If laboratory values from non-protocol specified laboratory assessments performed at the institution's local laboratory require a change in participant management or are considered clinically significant by the investigator (e.g., SAE or AE or dose modification), then the results must be recorded in the CRF or equivalent.
- Refer to the PAREXEL SOPs for appropriate processing and handling of samples to avoid duplicate/ and or additional blood draws.

#### **9.4.5. Suicidal Risk Monitoring**

Ciprofloxacin is considered to be a CNS-active drug. There have been some reports of rare instances of psychiatric reactions such as depression and psychosis leading to suicidal ideation as reported in the product label [[CIPROXIN Package Insert, 2016](#)] in some patients being treated with ciprofloxacin for bacterial infections. This risk is expected to be lower with a single dose versus a course of treatment. Nevertheless, GSK considers it important to monitor for such events before and during clinical studies with compounds such as this.

Study participants receiving ciprofloxacin should be appropriately observed for suicidal ideation and behaviour or any other unusual changes in behaviour. Consideration should be given to discontinuing further dosing with the study medication in participants who experience signs of suicidal ideation or behaviour.

## 9.5. Pharmacokinetics

Pharmacokinetic sampling time-points are discussed in the SoA in Section 2.

- Whole blood samples of approximately 6 mL will be collected into lithium heparin tubes, for measurement of plasma concentrations of ciprofloxacin as specified in the SoA. A maximum of 2 samples may be collected at additional time points during the study if warranted and agreed upon between the investigator and the sponsor. Instructions for the collection and handling of biological samples is provided in the PAREXEL Laboratory Manual. The actual date and time (24-hr clock time) of each sample will be recorded.
- Samples will be used to evaluate the PK of ciprofloxacin.
- Each plasma sample will be divided into 2 aliquots of not less than 1.2 mL plasma each (one for analysis and one backup).
- Samples collected for analyses of ciprofloxacin plasma concentration may also be used to evaluate safety related to concerns arising during or after the study.
- Pre-dose PK samples will be collected within 15 minutes prior to dose
- Post dose samples for 0.50-2.00 hrs will be collected within  $\pm$ 2 minutes ; samples for 2.50 – 8.00 hrs will be collected within  $\pm$ 5 min; and samples for 12.00 – 24.00 hrs will be collected within  $\pm$  10 min.
- Samples collected outside these recommended time windows will be recorded as protocol deviations
- Participant confidentiality will be maintained. At visits during which whole blood samples are also taken for laboratory or other tests, one sample of sufficient volume can be used.
- A validated bioanalytical method, as described in the PAREXEL bioanalytical protocol will be used for quantitative analysis.

## 9.6. Pharmacodynamics

Pharmacodynamic parameters are not evaluated in this study.

## 9.7. Genetics

Genetics are not evaluated in this study.

## 9.8. Biomarkers

Biomarkers are not evaluated in this study.

## 9.9. Health Economics OR Medical Resource Utilization and Health Economics

Health Economics/Medical Resource Utilization and Health Economics parameters are not evaluated in this study.

## 10. STATISTICAL CONSIDERATIONS

Refer to Analysis Plan ([Appendix 6](#)).

### Bioequivalence

The primary objective of this study is to demonstrate BE between the test 500 mg tablet formulation GR37547 and the reference formulation, based on PK endpoints  $C_{max}$  and  $AUC_{(0-t)}$  of ciprofloxacin.

The null hypothesis is that the true ratio of the geometric mean of the test treatment to the geometric mean of the reference treatment,  $\mu_{(Test)}/\mu_{(Reference)}$ , for the  $C_{max}$ , or  $AUC_{(0-t)}$ , is either  $<0.80$  or  $>1.25$  for plasma ciprofloxacin.

The alternate hypothesis is that the true ratio of the geometric mean of the test treatment to the geometric mean of the reference treatment for both the  $C_{max}$ , and  $AUC_{(0-t)}$ , is  $\geq 0.80$  and  $\leq 1.25$  for plasma ciprofloxacin.

Symbolically this is expressed as follows:

$$H_0: \mu_{(Test)}/\mu_{(Reference)} < 0.80 \text{ or } \mu_{(Test)}/\mu_{(Reference)} > 1.25$$

i.e., treatments are not bioequivalent.

versus

$$H_a: 0.80 \leq \mu_{(Test)}/\mu_{(Reference)} \leq 1.25$$

i.e., treatments are bioequivalent.

For each PK parameter designated as a primary endpoint, a two one-sided t-test (TOST)[[Schuirmann, 1987](#)] procedure with  $\alpha=0.05$  for each one-sided test will be used to test this set of hypotheses. Bioequivalence will be declared if the 90% CI for the true ratio of test to reference geometric means falls entirely within the range of 0.80 to 1.25 for all primary parameters.

For BE to be declared, the null hypothesis must be rejected, for all primary parameters  $C_{max}$ , and  $AUC_{(0-t)}$ , for ciprofloxacin.

## 10.1. Sample Size Determination

Sample Size Rationale:

Bioequivalence is to be determined on the basis of the endpoints  $C_{max}$  and  $AUC_{(0-t)}$  of ciprofloxacin.

Intra participant coefficient of variation ( $CV_w$ ) estimates in recent published data for ciprofloxacin were in the range of 12 to 18% for the primary endpoints of ciprofloxacin [Hassan, 2007; Cuadrado, 2004] which are in line with older published data [Galicia, 1998]. For the oral formulation,  $AUC$  data ( $CV_w$  approximately 11-12%) generally were less variable than  $C_{max}$  data (15-18%) and thus the latter should be considered for sample size calculation.

Hence, the sample size for this trial was determined based on maximum observed intra participant CV of 18%.

Based on a BE range of 80.00% to 125.00% for  $C_{max}$  and  $AUC_{(0-t)}$ , for ciprofloxacin assuming intra participant CV to be 18% and a "test/reference" mean ratio of 0.95; 22 evaluable subjects are needed to achieve a power of 90% at an alpha level of 0.05 for the single test for testing BE.

Approximately 26 eligible participants (approximately 19% in excess of number needed to complete) will be entered into the study to complete the study with at least 22 evaluable participants. See Section 5.2

## 10.2. Populations for Analyses

For purposes of analysis, the following populations are defined:

**Table 6 Description of Populations for Analysis**

Population	Description
Enrolled	All participants who sign the ICF
Randomized	All participants assigned to study treatment
Safety	All randomized participants who received at least 1 dose of study treatment. Participants will be analyzed according to the treatment they actually received.
PK	All subjects who complete the study and for whom primary PK parameters can be calculated for all treatment periods will be included in the statistical PK analysis of the study.

## 10.3. Statistical Analyses

The statistical methodology below describes the statistical analysis as it is foreseen when the study is being planned.

If circumstances should arise during the study rendering the analysis inappropriate, or if in the meantime improved methods of analysis should come to light, different analyses may be made. Any deviations from the statistical methodology, reasons for such deviations and all alternative or additional statistical analyses that may be performed, will be described in the clinical study report.

See [Appendix 6](#) for a list of Tables, Figures and Listings to be appended in the clinical study report.

### **10.3.1. PK Analyses**

Pharmacokinetic analysis will be the responsibility of the PAREXEL Quantitative Clinical Development (QCD) department. Plasma ciprofloxacin concentration-time data will be analysed by non-compartmental methods with Phoenix WinNonlin 6.3. The PK parameters will be calculated for each participant and treatment using non-compartmental analysis and using the actual sampling time intervals (relative to IMP administration) recorded during the study.

From the plasma concentration-time data, the following PK parameters will be determined, as data permit: maximum observed plasma concentration ( $C_{max}$ ), time to  $C_{max}$  ( $t_{max}$ ), area under the plasma concentration-time curve [ $AUC(0-\infty)$  and  $AUC_{(0-t)}$ ], and apparent  $t_{1/2}$  of ciprofloxacin.

Participants who experience emesis during the course of the study will be deleted from the statistical analysis if vomiting occurred within 4 hrs which is approximately twice the median  $t_{max}$  [[CIPROXIN Package Insert, 2016](#)]. For participants with pre-dose plasma concentrations, their data may be included without any adjustments in all PK measurements and calculations if the pre-dose concentration is  $\leq 5\%$  of  $C_{max}$ . If the pre-dose value is  $> 5\%$  of  $C_{max}$ , the participant's data may be dropped from all BE evaluations.

The available concentration data of the participants excluded due to vomiting, and of those who did not complete the PK sampling will only be listed; it will not be presented in descriptive statistics or included in PK evaluations or formal statistical analysis.

Pharmacokinetic data will be presented in graphical and/or tabular form and will be summarized descriptively. All PK data will be archived by the study sponsor GSK.

Statistical analyses of the PK parameter data will be the responsibility of PAREXEL Biostatistics.

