**Table 1 Schedule of Activities**

Procedure	Screening (Day -21 to Day -1)	Treatment Periods 1 and 2			Follow-up (within approximately 7 days post last dose or at discontinuation)	Notes
		Day -1	Day 1	Day 2		
Informed consent	X					
Inclusion and exclusion criteria	X	X				Refer to Section 6 . Recheck clinical status before randomization. and
Admission to the Unit (domiciled)		X	X	X		Participants to be admitted on Day -1 of each treatment period, and discharged on Day 2.
Outpatient Visits	X					
Discharge				X		
Participants will be discharged from the unit after the collection of the 24 hour post dose PK sample, vital signs (VS), lab assessments and, urinalysis; following review by a doctor to assess participant safety.
 
At the end of treatment period 2, in addition to the other assessments taken at 24 hours post dose (Day 2), all participants will also have an ECG and urine pregnancy test (females), prior to discharge.
 
Participants who have normal safety assessment results at the end of treatment period 2 do not require a follow up.

Procedure	Screening (Day -21 to Day -1)	Treatment Periods 1 and 2			Follow-up (within approximately 7 days post last dose or at discontinuation)	Notes
		Day -1	Day 1	Day 2		
Follow up (Phone Call or Outpatient Visit)					X	If a participant's safety assessments (medical exam, VS, ECG, Lab assessments) are abnormal and clinically significant at Treatment Period 2 discharge, then a follow up phone call or outpatient clinic visit is required within 7 days. Enquiries on the participant's general health, including any AEs/SAEs/concomitant medication should be recorded in the medical notes.
Demography and Medical history (includes substance usage)	X					Substances: Drugs, Alcohol, tobacco and caffeine
Full physical examination including height and weight	X	X				Abbreviated physical exam (excluding height and weight) performed at Day -1
Past and current medical conditions	X	X				
Pregnancy test (WOCBP only)	X	X		X		Serum $\beta$ -hCG: at screening. Urine $\beta$ -hCG: at Day-1 and at the end of Treatment period 2 on Day 2 .
HIV, Hepatitis B and C screening	X					Testing for Hepatitis B (HBsAg) and Hepatitis C (HepC antibody) at screening is not required if this was performed within 3 months prior to first dose of study treatment. Participants, who are positive for Hepatitis C antibody due to prior resolved disease, must have a confirmatory negative Hepatitis C RNA test.

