## 5.2. Number of Participants

Approximately 26 participants will be randomized such that at least 22 evaluable participants complete the study.

Participants who withdraw or are withdrawn from the study will not be replaced, unless fewer complete the study than the estimated number of evaluable participants (see Section 10.1 ).

If a Participant is replaced, the replacement will be allocated the subject number of PPD plus the subject number being replaced (e.g., Subject PPD will be replaced by PPD). The subject numbers being replaced will be selected such that the replacement participants receive the same treatment sequence as the withdrawn participants and the sequence balance is maintained.

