## 5.3. Participant and Study Completion

A participant is considered to have completed the study if he/she has completed all phases of the study including the last scheduled procedure shown in the SoA.

The end of the study is defined as the date of the last visit of the last participant in the study or last scheduled procedure shown in the SoA for the last participant in the trial.

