## **Presentation of PK Data, Descriptive Statistics and PK Assessment**

This section describes outputs to be presented.

The actual blood sampling times and time deviations will be listed for each participant dosed, treatment and scheduled sampling time. A listing of plasma concentrations of ciprofloxacin treatment will be provided.

Summary table reflecting summary statistics (n, arithmetic mean, geometric mean, median, coefficient of variation, standard deviation, minimum and maximum) per treatment will be provided for plasma concentrations of ciprofloxacin

Concentrations below the lower limit of quantification (LLOQ) will be indicated as below the limit of quantification (BLQ). These BLQ concentrations will be handled as follows:

- For descriptive statistics, pre-dose BLQ concentrations will be substituted by zeros. All other BLQ values will be substituted by  $\frac{1}{2}$ LLOQ value before the calculation of the summary statistics. Values reported as 'NS' (no sample) will be set to "missing".
- For PK assessment, all BLQ values at pre-dose and in the absorption phase, before the first reported concentration, will be substituted by zeros. The BLQ values between evaluable concentrations will be substituted by  $\frac{1}{2}$ LLOQ, before the calculation of the PK parameters. The terminal BLQ values will be set to missing. These measures are taken to prevent an over-estimation of AUC.

- For PK calculations, missing concentrations will be deleted, resulting in an interpolation between the nearest two concentration values.

A listing for PK parameters of ciprofloxacin per treatment will be provided. A summary table reflecting summary statistics (n, arithmetic mean, geometric mean, median, coefficient of variation, standard deviation, minimum and maximum) per treatment will be provided for PK parameters of ciprofloxacin.

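### Does the undefined exclusion for incomplete PK sampling leave the bioequivalence analysis set open?

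*Combined protocol and SAP*

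**What the plan says.** Three places bear on who enters the primary analysis.

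- **Section 10.2, Table 6** defines the PK population as "All subjects who complete the study and for whom primary PK parameters can be calculated for all treatment periods". Section 5.3 counts a participant as having completed the study after having "completed all phases of the study including the last scheduled procedure shown in the SoA". Neither requires every PK draw.
- **Section 10.3.1** keeps two groups out of descriptive statistics, PK evaluation and formal analysis: those excluded for vomiting, and "those who did not complete the PK sampling will only be listed". The second group is not defined.
- **Appendix 6** (presentation of PK data) sets values reported as NS (no sample) to missing for descriptive statistics. For PK calculations it says that "missing concentrations will be deleted, resulting in an interpolation between the nearest two concentration values".

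Section 5.2 does not replace withdrawn participants "unless fewer complete the study than the estimated number of evaluable participants".

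**The concern.** Take a participant who is dosed twice, gives the 24 h sample in both periods and misses one mid-profile draw. Table 6 and Appendix 6 keep that person. Section 10.3.1, taken at its most literal, removes them. In a pivotal bioequivalence study, membership of the primary set should follow from the text. This study is also open label, and no section says when the set is fixed relative to release of the concentrations.

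Three smaller points add to the impression:

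- The replacement rule counts completers, so exclusions made under Section 10.3.1 might take the evaluable number below 22 without triggering replacement.
- A participant with full PK data could be lost for missing a safety contact, because completion is tied to the last scheduled procedure.
- The rule for a pre-dose value above 5% of Cmax is discretionary: such a participant's "data may be dropped from all BE evaluations".

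At stake would be lost power, or a choice of analysis set made with the results in hand.

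**Working it through.** **1. Reading the rules together.** Appendix 6 gives a rule for NS values in descriptive statistics and a rule for missing concentrations in PK calculations. Section 10.3.1 bars those who did not complete sampling from both. If one missed draw counted as non-completion, the NS rule would have almost nothing to act on. The reading that leaves every rule a purpose is that isolated gaps follow Appendix 6 and broken-off sampling follows Section 10.3.1.

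**2. The plan's own figure.** Inputs from Section 10.1: CV 18%, ratio 0.95, limits 0.80 to 1.25, one-sided alpha 0.05. Table 5 gives 13 participants per sequence.

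- Within-participant SD on the log scale: sqrt(ln(1 + 0.18²)) = 0.1786.
- SE of the treatment difference: 0.1786 × sqrt(0.5 × (1/n1 + 1/n2)). At n = 22 this is 0.1786 × sqrt(0.0909) = 0.0538, with df = 20.
- Power of the two one-sided tests, integrated over the distribution of the residual variance:

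| n | 18 | 20 | 22 | 24 | 26 |
|---|---|---|---|---|---|
| Power | 86.5% | 89.9% | 92.4% | 94.3% | 95.8% |

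The smallest balanced n reaching 90% is 22, as stated.

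**3. How often the reading changes the verdict.** For each case, 200,000 crossovers with n = 26 were simulated at the planning values, and k participants were removed at random.

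| k in dispute | Verdict differs | Pass to fail | Fail to pass (difference) |
|---|---|---|---|
| 1 | 1.7% | 1.2% | 0.5% |
| 2 | 2.6% | 2.0% | 0.6% |
| 3 | 3.7% | 3.1% | 0.6% |
| 4 | 4.7% | 4.0% | 0.7% |

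As a check, at k = 4 the net loss is 4.0 − 0.7 = 3.3 points, against 95.8 − 92.4 = 3.4 from the exact power. At an assumed CV of 25%, outside the 12 to 18% in Section 10.1, the verdict differs in 5.6% to 13.4% of trials.

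**4. How many participants could be in dispute.** There are 17 draws per period, so 34 per participant. With an assumed independent miss rate p, the expected number with at least one miss is 26 × [1 − (1 − p)^34]. This gives 1.7 at p = 0.2% and 4.1 at p = 0.5%. Under the literal reading the chance of fewer than 22 remaining is 0.2% at p = 0.1%, 38.7% at 0.5% and 91.0% at 1%. The documents give no miss rate. Participants are resident from Day −1 to Day 2 and are discharged after the 24 h sample, and a removed cannula is replaced or venepuncture is used (Tables 1 and 2).

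**5. The unsettled boundary: a missed 24 h draw.** Interpolation cannot fill it, but AUC(0-t) to the last quantifiable concentration (Section 10.3.3.1) is still calculable. On illustrative one-compartment profiles (half-life 4 to 7 h, assumed absorption rates) that participant's AUC falls by 3.4% to 9.7% in that period. With 13 per sequence, each participant's log difference has weight 1/26. The shift in the log ratio is therefore ln(0.966)/26 = −0.0013 to ln(0.903)/26 = −0.0039, or 0.1% to 0.4%. At a CV of 12%, the upper end of the range Section 10.1 gives for AUC, power is above 99.8% at n = 22.

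**6. Side points.**

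- *Replacement.* The synopsis, the opening of Section 5.2 and Section 10.1 all set the target as 22 evaluable participants, which tells the team what to count.
- *Safety contact.* Table 1 says "Participants who have normal safety assessment results at the end of treatment period 2 do not require a follow up". The loss requires a clinically significant abnormality at discharge and then a missed contact that may be a phone call, despite the contact attempts required by Section 8.3.
- *Pre-dose rule.* A 7-day washout at the longest stated half-life is 7 × 24 / 7 = 24 half-lives, so carry-over above 5% of Cmax is not a realistic event.

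**The case for a change.** The strongest reply is that the sensible reading is only implied. Nothing in the text says that incomplete sampling means broken-off sampling, and that reading does not settle a missed 24 h draw. The abbreviations list adds some doubt by tying AUC(0-t) to the last quantifiable time within a participant across treatments, which differs from Section 10.3.3.1. Describing the choice in the study report is not the same as specifying it beforehand, and a sentence of wording would cost nothing.

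The gap in wording stands, and so does the absence of a stated time for fixing the set. The inference to a vulnerable result does not. Missed draws are known when they occur, before any assay. Section 9.5 records actual sampling times and Section 10.3.2 tracks deviations throughout. Under the natural reading these participants stay in, so switching to the literal reading afterwards would rescue a failed trial in only 0.5% to 0.7% of cases. That figure was obtained at the planning ratio, not at a ratio on the equivalence limit, so it gauges exposure and is not a type I error rate. No bias or error inflation has been shown, and the losses modelled mostly work against the sponsor.

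**Conclusion.** No change follows. The exclusion in Section 10.3.1 lacks a definition, but Appendix 6 and Table 6 supply one that analysts would adopt: keep participants with isolated gaps, and exclude those whose sampling was broken off so that the primary parameters cannot be obtained. What remains open, mainly a missed 24 h draw, moves the AUC ratio by about 0.1% to 0.4% per participant affected. If all four surplus participants were lost, power would still be 92.4%, above the planned 90%; at 20 it is 89.9%.

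This rests on the planning ratio and CV, on missed draws being unrelated to formulation, and on misses being uncommon in resident participants. A miss rate near 1% per draw combined with the literal reading would cost real power (about 18 of 26 remaining, 86.5%), but that combination needs both an assumed rate and the reading that the plan's own missing-data rules argue against. The sample size is not in question.
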